2. STUDY DESIGN

2.1. Synopsis of Study Design

This was a prospective, randomized, double-blind, placebo-controlled study to demonstrate the efficacy and safety of linzagolix administered orally once daily at doses of 75 mg alone and 200 mg in combination with low dose ABT (E2 1 mg/NETA 0.5 mg) versus placebo in the management of moderate to severe EAP in women with surgically confirmed endometriosis.

The study started with an approximately 3-month screening period during which subjects received no study drug. Eligibility was confirmed based on data collected during the screening period. After randomization, patients entered a 6-month Treatment Period. Subjects were to be randomized to one of the three treatment groups:

1. Linzagolix 75 mg
2. Linzagolix 200 mg combined with ABT
3. Placebo

Randomization was conducted via an interactive web response system (IWRS) in a 1:1:1 ratio. There was no stratification.

[figure not shown]
At 6 months, BMD change was to be assessed via DXA measurement. Eligible subjects who had completed the 6-month treatment period were invited to enter a separate extension study for 6 additional months of active treatment (no placebo control). In this extension study, subjects who previously received placebo were to be randomly switched to one of the two active treatments (Linzagolix 75 mg alone (with ABT placebo) or Linzagolix 200 mg combined with ABT). Subjects who received active treatment were to continue with the same treatment.

Subjects who declined to participate to or did not qualify for the extension study and who were exposed to at least 3 months of treatment were to enter a 6-month drug-free follow-up. At the end of the 6-month follow-up period, subjects with a BMD decrease from baseline of >1.5% for lumbar spine and/or >2.5% for total hip were to had an additional DXA scan 6 months later. Subjects who discontinued treatment prior to Month 3 were not eligible to enter the follow-up period.

The study was to be on average 15 months; 3-month Screening Period, 6-month Treatment Period and 6-month Follow-up (with 1 month being defined as 28 days/4 weeks). The duration excluded any washout period.

Sponsor:	ObsEva		
Protocol:	18-OBE2109-002		
Document Version No.:	1.0	Document Date:	18-MAY-2021

A schematic of the study design is shown in Figure 1.

* Subjects who discontinue treatment prior to Month 3 will not enter the follow-up period.

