For other safety results, data from early discontinuation should be compared to theoretical visits dates. Only assessments within the window of theoretical date +/-14 days will be used for analyses, if it is planned to have a such assessment at this visit and no other assessment is in the window. If a subject discontinued in the main treatment period, date will be compared to the theoretical visit dates in main treatment period as described in Table 3. If a subject discontinued in the follow-up period, date will be compared to the theoretical visit dates in Follow-up period from

Sponsor:	ObsEva		
Protocol:	18-OBE2109-002		
Document Version No.:	1.0	Document Date:	18-MAY-2021

Table 4.

For unscheduled safety assessments, if the assessment occurs in a window of +/- 14 days of a planned eCRF visit for which it was planned per protocol to have such assessment, and no assessment was done for that visit, the assessment will be assigned to that visit. If the assessment is equally distant from two eCRF visits with no corresponding safety assessment, the assessment will be assigned to the next visit.

For biopsy, DXA assessment or laboratory assessment, if an assessment has been assigned in external data to a follow-up visit of the main study for subjects entered extension study, the visit of assessment should be reassigned with the same rules described above for unscheduled safety assessment.

Table 3 Theoretical Visit Dates in Main Treatment Period

Visit	Theoretical Date
Month 1	Day 29
Month 2	Day 57
Month 3	Day 85
Month 4	Day 113
Month 5	Day 141
Month 6	Day 169

Sponsor:	ObsEva		
Protocol:	18-OBE2109-002		
Document Version No.:	1.0	Document Date:	18-MAY-2021

Table 4 Theoretical Visit Dates in Follow-up

Visit	Theoretical Date
Month 1 FU	Month 6 date or treatment discontinuation date + 28
Month 2 FU	Month 6 date or treatment discontinuation date + 56
Month 3 FU	Month 6 date or treatment discontinuation date + 84
Month 4 FU	Month 6 date or treatment discontinuation date + 112
Month 5 FU	Month 6 date or treatment discontinuation date + 140
Month 6 FU	Month 6 date or treatment discontinuation date + 168

4.2.11. **Baseline Definition**

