4.2.12. Last treatment administration date, End of Study date and Period definitions

The last treatment administration date will be defined as the date of treatment termination recorded in the main period eCRF page. If this date is missing, the last date with a drug intake in eDiary prior to the Month 6 date or, for subjects who discontinued, the last date with available drug intake information in the subject eDiary will be used.

The end of study date will be the last assessment date in the main study defined as last eCRF or ediary date prior to and not including Month 6 for subjects who entered the Extension, and the last eCRF or ediary date in the main study or main follow-up if not. This will not necessarily be the same date as last assessment date as recorded in the eCRF.

Note: For summaries by visit (efficacy or safety), the Month 6 assessments will be included in the main study analyses. For Adverse Events, Concomitant Medications and Daily diaries, data collected on Month 6 date will be part of the extension for subjects entering the extension study and be part of the Follow-up period for subjects entering the main study follow-up period.

The main treatment period will be defined as Day 1 up to (Month 6 date -1) or the treatment discontinuation date.

The main follow-up period will be defined as the Month 6 date or (treatment discontinuation date+1) up to the end of study date (for subjects who entered into the main follow-up period).

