4.8.1.2. Compliance

Lingazolix/Placebo Grey blister (200 mg or matching placebo), Lingazolix/Placebo Pink blister (75 mg or matching placebo) and Add-back therapy compliance from the study treatment accountability page among the Day 1- End of main study treatment period will be summarized by treatment group.

If Lingazolix/Placebo and Add-back therapy compliances from accountability data are missing, compliance will be computed from daily diary data.

Compliance will be computed as the number of days with pink tablet/grey tablet/Add-back capsule taken *100 divided by the number of days in the period (Month 6 visit date/withdrawal date - Day 1). Data from “Today” will be used primarily. If data from today is missing, date from “Yesterday” will be considered. If the e-diary is not completed for a day (neither “Today” nor “Yesterday”), it will be assumed that no intake of drug was taken on that day.

Study treatment overdose and misuse will be reported in a listing.

Compliances will be reported in a listing.

Sponsor:	ObsEva		
Protocol:	18-OBE2109-002		
Document Version No.:	1.0	Document Date:	18-MAY-2021

4.8.2. **Adverse Events**

Adverse events will be coded using the Medical Dictionary for Regulatory Activities (MedDRA) and displayed in tables and listings using System/Organ/Class (SOC) and Preferred Term.

Analyses of adverse events will be performed for those events that are considered treatment emergent (TEAEs), where treatment emergent is defined as AEs with a start date on or after the first dose of study drug through 30 days after discontinuation of study drug or Month 6 visit date, or any event that was present at baseline but worsened in intensity or was subsequently considered drug-related by the investigator through the end of the study.

Adverse Event tables will be presented for the following periods: Day 1 to Month 6 (treatment period) and Month 6 to Month 6 FU (follow-up period) as defined in section 4.2.12.

Adverse events starting more than 30 days after end of treatment will be considered as post-treatment AE.

Note: if an adverse event started after or at Month 6 visit date and if the subject entered the extension period, this adverse event will not be displayed for the main study, but only for the extension study.

For each of these 2 study periods, an overall summary table will be prepared presenting, by treatment group and overall, the number and percentage of subjects with

- any AE,
- any TEAE,

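### For subjects who stop treatment before Month 3, treatment-emergent adverse events starting after the discontinuation date and within 30 days fall in no adverse-event table, only in listings

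*SAP*

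**What the plan says.** SAP 4.8.2 lets the treatment-emergent window run from first dose "through 30 days after discontinuation of study drug or Month 6 visit date". It then limits the tabulations: "Adverse Event tables will be presented for the following periods: Day 1 to Month 6 (treatment period) and Month 6 to Month 6 FU", and it sends the reader to SAP 4.2.12 for the definition of both periods.

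In SAP 4.2.12 the first period closes early for anyone who stops: "The main treatment period will be defined as Day 1 up to (Month 6 date -1) or the treatment discontinuation date". The follow-up period opens on the next day and runs "up to the end of study date (for subjects who entered into the main follow-up period". The same section has a separate rule for last dose: "The last treatment administration date will be defined as the date of treatment termination recorded in the main period eCRF page", with an eDiary fallback. It does not say whether the treatment discontinuation date is that date or another one.

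SAP 2.1 settles who can have a second period. "Subjects who discontinued treatment prior to Month 3 were not eligible to enter the follow-up period". The extension is closed to them as well: "Eligible subjects who had completed the 6-month treatment period were invited to enter a separate extension study". SAP 3.1 builds the Follow-up Safety Set on the same eligibility.

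In SAP Appendix B every adverse-event table is either Day 1 to Month 6 on the Safety Analysis Set, or Month 6 to Month 6 FU on the Follow-up Safety Set. The adverse-event listings use the Safety Analysis Set with no period limit.

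**The concern.** After early termination, safety is the only analysis left, and SAP 2.1 says it covers all subjects however long they were treated. Women who stop in the first three months are a group in whom events just after stopping matter, and the SAP's own window was drawn to include those events. Protocol 13.5.5 removes from the treatment-emergent summaries only events that start more than 30 days after stopping. SAP section 5, which declares departures from the protocol, mentions no narrowing of that rule.

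A programmer who follows SAP 4.2.12 literally would flag such an event as treatment-emergent and then find no table period to put it in. A reader of tables titled Day 1 to Month 6 would assume that those calendar days are covered. At stake is an undercount by arm in the any-event, serious, fatal and related rows. The data themselves are not lost.

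**Working it through.** The plan states no figure to reproduce. The check assigns onset days to tables under the SAP's rules.

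**Inputs.** Treatment-emergent window: last dose + 30 days (SAP 4.8.2). End of treatment period for a discontinuer: treatment discontinuation date (SAP 4.2.12). Follow-up period: entrants only (SAP 4.2.12, 3.1). Month 3 visit: Day 85 ± 3 (protocol 10.2.2.3). Month 6: Day 169 (SAP Table 3).

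**Step 1: assign each of the 30 onset days after stopping, taking the discontinuation date as last dose.**

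| Stops on | Enters follow-up | Treatment tables | Follow-up tables | No table |
|---|---|---|---|---|
| Day 15, 29, 57 or 84 | No (not eligible) | 0 | 0 | 30 |
| Day 86, 113 or 141 | Yes | 0 | 30 | 0 |

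**Step 2: let the discontinuation date fall w days after last dose.** The gap is max(0, 30 − w) days. The lags below are assumptions, since the documents give none.

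- w = 0: 30 days
- w = 7: 30 − 7 = 23 days
- w = 14: 30 − 14 = 16 days
- w = 28: 30 − 28 = 2 days
- w ≥ 30: none

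**Step 3: are the affected days inside the span the titles name?** The latest Month 3 visit is Day 85 + 3 = Day 88, so the latest earlier dose is Day 87. The last affected day is 87 + 30 = Day 117, which is 169 − 117 = 52 days before Month 6. All affected days lie inside the titled span.

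**Step 4: which events can reach the database?** Under protocol 5.6 and 10.7.2, a subject who stops before Month 3 has one withdrawal visit and then leaves the study. Protocol 12.3.2 adds serious events the site becomes aware of up to 4 weeks (28 days) after treatment stops. The events exposed to the gap are therefore mainly those starting between last dose and the withdrawal visit, plus such later serious events.

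**Step 5: effect on the counts.** SAP 4.8.2 counts a subject once per row. A row loses her only if she has no other qualifying event there. For example, a discontinuer with one on-treatment event and one serious event after last dose stays in the any-event row but is missing from the serious row. SAP 4.8.2 also tabulates numbers of events, and there each omitted event lowers the count by 1. The summary rows for any adverse event and any serious adverse event do not rescue it, because that table too is prepared separately for each of the two periods.

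**The case against.** The best reply is that the discontinuation date may not be last dose. SAP 4.2.12 uses that term and last treatment administration date side by side as if they differ, and SAP 4.8.1.2 ends a discontinuer's compliance period at the withdrawal date. SAP Table 4 places the Month 1 follow-up visit at "Month 6 date or treatment discontinuation date + 28" days, where protocol 10.2.3.1 counts 28 days from last intake. That points to last dose, but it concerns subjects who have follow-up visits, which these subjects do not. This objection stands against any fixed size: 30 days is an upper limit.

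A second reply is that little is collected after the withdrawal visit. This also stands, and it narrows the affected events as in step 4 of the working. It does not remove them, because the interval from last dose to that visit and the serious-event duty both remain.

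A third reply reads the table titles as calendar time, so that an event on Day 60 counts whenever drug stopped. This fails on the text, because SAP 4.8.2 ties the periods to SAP 4.2.12. If calendar time is intended, the definition still has to change.

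Finally, no hypothesis is tested and every event stays in the listings, serious and fatal ones included. That limits the consequence, but it does not make the tables agree with the SAP's own window.

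**Conclusion.** The mismatch is real. As written, treatment-emergent events of subjects who stop before Month 3 that start after the discontinuation date and within 30 days are in no adverse-event table, contrary to protocol 13.5.5 and undeclared in SAP section 5. The gap per subject is at most 30 days if the date means last dose, and shorter or nil if it means a later withdrawal date. The documents give neither the number of affected subjects nor the number of events, and both may be small.

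A reader might infer three stronger things that the documents do not support:

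- A full 30 days is always lost. The date is undefined, and routine collection largely ends at the withdrawal visit.
- The SAP deliberately hides early harm, or data are lost. The listings keep every event, and nothing shows intent.
- The gap reaches other subjects. Follow-up entrants have these events in the follow-up tables, and extension entrants in the extension study. A later stopper or a completer with neither would be caught too, but the documents show none.

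Because these tables are the main remaining product of the trial and the repair is small, it should be made before they are produced.

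**What to change.** In SAP 4.2.12, define the treatment discontinuation date as the last treatment administration date already defined there.

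In SAP 4.2.12 and 4.8.2, for Safety Set subjects who enter neither follow-up nor the extension, assign adverse events starting up to 30 days after last dose to all Day 1 to Month 6 adverse-event tables: 14.3.1.1.1, 14.3.1.2.1, 14.3.1.3.1, 14.3.1.4.1, 14.3.1.5.1, 14.3.1.6.1, 14.3.2.1.1, 14.3.2.3.1 and 14.3.2.4.1. Table 14.3.2.3.1 (events leading to permanent discontinuation) must be included. Once the date means last dose, an event starting the next day can still be the reason drug is not resumed. It would then be counted in the matching row of Table 14.3.1.1.1 but not in Table 14.3.2.3.1.

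Add a footnote giving the number of subjects and events added, and stating that off-drug days are included for these subjects only.

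The cost is SAP wording, one change to the period flag using onset dates already collected, and the footnote. Under step 1 of the working, all 30 of 30 onset days would then be tabulated, against 0 of 30. The downside is that up to 30 off-drug days enter the treatment-period tables for this subgroup, while the same interval goes to the follow-up tables for follow-up entrants. The footnote makes that difference visible.

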4.3. Interim Analyses

Not applicable

Sponsor:	ObsEva		
Protocol:	18-OBE2109-002		
Document Version No.:	1.0	Document Date:	18-MAY-2021

4.4. **Subject Disposition**

A tabulation of subject disposition will be presented by treatment group and overall, for randomized subjects and for safety population, including :

- Number of subjects screened, and reasons for screen failures,
- Number of subjects randomized,
- Number of subjects discontinued study between randomization and Day 1,
- Number of subjects who received at least one dose of study drug,
- Number of subjects who completed treatment period until Month 6
- Number of subjects who discontinued treatment period between Day 1 and Month 3 visit (included), and reasons for treatment discontinuation
- Number of subjects who discontinued treatment period between Month 3 visit and Month 6 (included), and reasons for treatment discontinuation
- Number of subjects who entered follow-up period
- Number of subjects who discontinued follow-up period, and reasons for follow-up discontinuation
- Number of subjects who completed the study

Note that subjects who completed the treatment period and entered in the extension study will be considered as completed the study. For the other subjects, a subject will be considered as completed the study if the subject complete the treatment period and the follow-up period.

- Number of subjects who entered in the extension study

The number in each subject population for analysis will be presented by treatment group and overall, for randomized subjects. The number of subjects who completed each visit will be summarized by treatment group and overall, for the Safety population.

The number of subjects screened and randomized by country and by site will be also provided.

The following listings will be presented:

- Study completion information, including the reason for premature study withdrawal, if applicable;
- Inclusion/exclusion criteria for Screened Subjects;
- Subject inclusion in each of the analysis sets (Safety Analysis Set and Follow-up Safety Set) and reasons of exclusion

Sponsor:	ObsEva		
Protocol:	18-OBE2109-002		
Document Version No.:	1.0	Document Date:	18-MAY-2021

4.5. Demographic and Baseline Characteristics

Baseline, demographic and medical history information will be analyzed for the safety set.

No formal statistical comparisons will be performed.

4.5.1. Demographics

Demographics and baseline characteristics will be summarized by treatment group and overall using descriptive statistics.

Demographics and baseline data include Age (years), Gender, Ethnicity, Race, Height (cm), Weight (kg), Body Mass Index (kg/m²), Systolic Blood Pressure (mmHg), Diastolic Blood Pressure (mmHg), Heart Rate (beats/minute), QTc interval (Fridericia) (ms).

BMI is auto-calculated, defined as: Weight (kg)/(Height(m)*Height(m)).

Demographic and Baseline data will be provided in data listings.

4.5.2. Baseline Disease Characteristics

The definition of the two baseline menstrual cycles is described in section 4.2.11.

Baseline Dysmenorrhea (DYS) and Non-Menstrual Pelvic Pain (NMPP) will be calculated by averaging over the two baseline menstrual cycles, the e-diary daily answers of Endometriosis Related Pelvic Pain (PP VRS Questionnaire). Responses of "None," "Mild," "Moderate," and "Severe" will be assigned a score of 0, 1, 2, and 3, respectively. Dysmenorrhea will be computed using days with uterine bleeding, defined as those days on which the subject records any uterine bleeding or spotting in the subject eDiary; Non-Menstrual Pelvic Pain will use days with no uterine bleeding. Note that days with missing information on bleeding will not be used for analysis.

The baseline analgesic use will be calculated as the mean of daily pill count of analgesics over the two baseline menstrual cycles for each class of rescue analgesics (endometriosis-associated: Ibuprofen, Narcotic Analgesic) collected in the eDiary, separately for bleeding days, non-bleeding days and overall.

Dysmenorrhea, Non-Menstrual Pelvic Pain and Analgesic use will be summarized as continuous variables

The average duration of the two baseline menstrual cycles (days) will be summarized. The duration (days) of the two individual baseline menstrual cycle will be calculated using the menstrual period diaries (menstrual start date confirmed by subject). The duration is computed as (start date of Cycle_{x+1} – start date of cycle).

The average number of days with uterine bleeding over the two baseline menstrual cycles will be summarized as continuous variables.

The number and percentage of subjects with Normal, Abnormal, Abnormal clinically significant (or Not Assessable) results for Physical Examination, Gynecological Examination, Breast Examination, Mammography, Endometrial Biopsy and PAP Smear assessments will be presented by treatment group and overall. Abnormality details will be provided in data listings.

Sponsor:	ObsEva		
Protocol:	18-OBE2109-002		
Document Version No.:	1.0	Document Date:	18-MAY-2021

Transvaginal ultrasound data (i.e., presence of ovarian endometrioma with a diameter of 7 cm or greater, uterus length, width, and depth in mm and corresponding calculated uterine volume in cm³ (using the prolate ellipsoid formula [L x H x W x 0.523]), endometrium thickness in mm, and presence of any uterus abnormality (Fibroids, Adenomyosis, other), left ovary or right ovary abnormality) will be summarized.

Dysmenorrhea, Deep Dyspareunia, Non Menstrual Pelvic Pain, Total Pelvic Pain (None: 0, Mild: 1-3, Moderate: 4-6, Severe: 7-9), Pelvic Tenderness, Induration, Total Physical Sign Score (None: 0, Mild: 1-2, Moderate: 3-4, Severe: 5-6) and Composite Pelvic pain and Physical Sign Score (None: 0, Mild: 1-2, Moderate: 3-5, Severe: 6-10, Very Severe 11-15) from the Modified Biberoglu & Behrman symptom severity scale assessment as collected in eCRF will be summarized at baseline as categorical variables with the following categories: None, Mild, Moderate, Severe (Very Severe).

Baseline Disease Characteristics will be reported in listings.

4.5.3. Medical History

Medical history will be summarized by System Organ Class and Preferred Term using the Medical Dictionary for Regulatory Activities (MedDRA), by treatment group and overall.

Medical history is summarized by subject incidence rates; therefore, a subject contributes only once to the count for a given medical history (SOC or preferred term).

Medical history will be reported in a listing.

4.5.4. Endometriosis History

Time since first medical diagnosis/treatment, first surgical diagnosis and most recent surgical diagnosis in years defined as (randomization date – date of diagnosis)/365.25 will be summarized.

Presence within 2 months before screening and ongoing symptoms of the following symptoms will be summarized, by treatment group and overall: Dyspareunia, Dyschezia, Dysuria, Adenomyosis, Rectovaginal endometriosis nodes.

Endometriosis History will be reported in a listing.

